3.2. Study Endpoints

3.2.1. Primary Endpoints

Primary efficacy endpoint: Effective closure rate at 360-day post operation:

Effective closure is defined as no or only a trivial to small residual shunt (based on left-to-

right Doppler flow signals with a diameter <5mm) as assessed by TTE or TEE after device implantation.

Primary safety endpoint: Rate of common complications during 360 days post operation:

Common complications include occluder displacement, high-grade atrioventricular block, cardiac tamponade, air embolism, moderate or larger residual shunt, intractable headache or migraine, and cerebral embolism.

3.2.2. Secondary Endpoints

Immediate operation success rate, which means that left and right disks are effectively fixed on the left and right sides of the atrial septum, respectively, and smoothly released without displacement or migration, and the delivery system is successfully withdrawn.

3.2.3. Other Safety Endpoints

- Incidence of device-related Adverse Events (AE);
- Incidence of Serious Adverse Events (SAE);
- Lab test indicator;
- 12-lead ECG indicator;
- Imaging examination (Chest X-ray and Echocardiography)
- Vital signs indicator.

4. STATISTICAL CONSIDERATION

For continuous variables, the following will be listed: number of valid cases, mean, standard deviation, median, 25th and 75th percentiles, minimum value, and maximum value. The number of decimal places for the 25th and 75th percentiles, minimum, and maximum values will match the records in the database. The mean and median will retain one more decimal place than the raw data recorded in the database, while the standard deviation will retain two more decimal places than the raw data recorded in the database.

For categorical variables, data will be presented in frequency tables (frequencies and percentages). Percentages will be rounded to one decimal place. When the frequency is zero, only the frequency needs to be listed; the percentage may be omitted to distinguish it from non-

zero values. When calculating percentages, the number of subjects in the specified analysis population will serve as the denominator.

All hypothesis tests employ one-sided tests unless otherwise specified, with a statistical significance level of $\alpha=0.025$. Differences are considered statistically significant when $P<0.025$. All confidence intervals were calculated at the 95% confidence level. P-values were rounded to three decimal places. If $P < 0.001$, the value was output as “<0.001”. If $P > 0.999$, the value was output as “>0.999”.

All analyses in the safety evaluation are based on observed data, without considering data imputation. For table analyses based on the safety analysis set, all subjects receiving at least one treatment with the study device will be included in the analysis. However, for listing analyses, all subjects with safety evaluations will be included, even if they did not receive any trial treatment.

Unless otherwise specified, baseline data shall be defined as the last valid measurement taken before the implant procedure.

When multiple observation data points exist for the same examination at the same follow-up time point, the observation closest in time to the scheduled visit date will be designated as the primary analysis record for the relevant statistical analysis.

Statistical analysis was performed using SAS 9.4[®] software. Subject information and safety databases were exported and stored in SAS XPORT format.

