8.7.2 Missing and unreasonable data

The trial should ensure that the data records are 100% correct, especially the primary endpoints. For missing, unused and irrational data or data of withdrawal subjects, strict review should be conducted. The basic statistical principles for processing these data are as follows:

- (1) The details of each dropout subject will be described;
- (2) The last observation carried forward (LOCF) method will be applied for the missing values of the main evaluation indicators;
- (3) The missing values of qualitative or quantitative secondary endpoints are not carried forward, and are

handled according to the missing values;

- (4) The missing values of all safety endpoints are not carried forward, and are handled according to the missing values.

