6. SAFETY ANALYSIS

Safety evaluation endpoints include adverse events, laboratory test results, electrocardiogram (ECG) results, imaging assessments (chest X-ray and echocardiography), and vital signs. All safety endpoints will be analyzed descriptively based on the SS.

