6.1.1. Treatment-emergent Adverse Events

All TEAEs will be summarized by System Organ Class (SOC) and Preferred Term (PT), and the incidence will be presented accordingly. At each level of summarization, if a subject experiences one or more adverse events within a given category, the subject will be counted only once and will not be counted repeatedly. All percentages will be calculated using the total number of subjects in the SS as the denominator.

If the relationship of an adverse event to the investigational device or the procedure is unclear, it will be classified as related for analysis purposes. In the categorization of relationship to the investigational device or procedure, events assessed as possibly related, probably related, or definitely related will be grouped as related, whereas events assessed as not related or unlikely related will be grouped as unrelated.

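### SAP section 4's whole-population denominator, if applied to by-visit categorical safety results, can understate abnormality rates by the share of missing assessments

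*SAP*

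**What the plan says.** SAP section 4 closes its paragraph on categorical variables with a rule that has no exceptions: "When calculating percentages, the number of subjects in the specified analysis population will serve as the denominator". For continuous data it is more careful: "For continuous variables, the following will be listed: number of valid cases". Nothing equivalent is asked for categorical data, neither a number assessed nor a row for missing.

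The same section says of missing safety data: "All analyses in the safety evaluation are based on observed data, without considering data imputation". For tables on the SS, it says that "all subjects receiving at least one treatment with the study device will be included in the analysis". Protocol 8.7.2 agrees on missing values: "The missing values of all safety endpoints are not carried forward, and are handled according to the missing values".

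SAP section 6 covers adverse events, laboratory tests, ECG, chest X-ray, echocardiography and vital signs, and states: "All safety endpoints will be analyzed descriptively based on the SS". For adverse events, section 6.1.1 repeats the denominator explicitly: "All percentages will be calculated using the total number of subjects in the SS as the denominator".

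The primary endpoints have their own rule. SAP 4.2, 5.1.1 and 5.1.2 apply non-responder imputation, so that in the FAS a subject with missing data counts as a closure failure or as having had a complication.

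**The concern.** A whole-set denominator suits cumulative adverse event incidence, where each subject is followed for events and counted once. It does not suit a finding that can be seen only if the examination took place, such as arrhythmia type on an ECG or residual shunt on an echocardiogram at a given visit. A subject not examined at that visit stays in the denominator and cannot enter the numerator of any category.

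The trial has one arm. No concurrent group would show the same dilution, so readers will take the absolute percentages and their course over time at face value. If missing assessments accumulate, a stable arrhythmia or shunt rate would appear to decline. For an absorbable implant followed to five years, that course over time is what the descriptive tables are meant to show.

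**Working it through.** The documents give no by-visit safety percentage, so there is no figure of the plan to reproduce. The check has two parts: whether the rule would reach by-visit results, and what it would then do.

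**Does the rule reach by-visit results?**
- SAP section 4 selects one record when an examination is repeated around a follow-up time point (the one nearest the planned date). That is needed only for per-visit summaries.
- The schedule in Protocol 7.2.2 places TTE, ECG and vital signs at all nine follow-up visits, to year 5. Laboratory tests end at 3 years and chest X-ray at 360 days.
- Protocol 8.7.4 asks for counts and proportions by arrhythmia type, and for occlusion as judged on imaging.
- The only general denominator in the SAP is the one in section 4.

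By-visit use is therefore a fair inference. It remains an inference, because the available SAP text ends at section 6.1.1 and shows no such tables.

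**What does it do?** Let N be the number in the SS, n the number assessed at the visit, x the number with the finding, and m = (N − n)/N the missing share.

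- Observed rate: r = x/n
- Printed rate: x/N = r × n/N = r × (1 − m)
- Relative understatement: (r − r(1 − m))/r = m

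Inputs from the documents: planned N of 142 (SAP 3.1) or 146 (Protocol 8.2.1), and a maximum expected dropout of 20% (Protocol 8.4). Assumptions: the SS equals the planned N; the observed abnormality rate is 10%; the missing share runs from 0 to 20%.

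For N = 142:

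| Missing share (about) | Assessed n | Abnormal, observed | Abnormal, printed | Normal, observed | Normal, printed | Printed sum |
|---|---|---|---|---|---|---|
| 0% | 142 | 10% | 10.0% | 90% | 90.0% | 100.0% |
| 5% | 135 | 10% | 9.5% | 90% | 85.6% | 95.1% |
| 10% | 128 | 10% | 9.0% | 90% | 81.1% | 90.1% |
| 20% | 114 | 10% | 8.0% | 90% | 72.3% | 80.3% |

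With N = 146 (n = 146, 139, 131 and 117), the printed abnormal rates are the same to one decimal: 10.0%, 9.5%, 9.0% and 8.0%. At 20% missing, an observed 5% prints as 4.0% and an observed 20% as about 16%.

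Read down the table, the observed rate is constant while the printed rate falls from 10.0% to 8.0%. That is the spurious trend.

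An illustration in whole subjects: of N = 146, 117 are assessed and 12 have the finding. The observed rate is 12/117 = 10.3% and the printed rate 12/146 = 8.2%. Normal results go from 105/117 = 89.7% to 105/146 = 71.9%. The other 29/146 = 19.9% are in no category.

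**The case against.** The strongest reply is that the affected tables are not in the SAP text, so the concern turns a general convention into a statement about specific outputs. Protocol 8.7.4 gives laboratory tests a continuous summary and a listing of clinically significant abnormal values. It names no visit and no denominator for the ECG and imaging proportions. This stands as a limit on certainty. It does not remove the point, because a programmer following section 4 would have no other denominator to use.

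A second reply is that the shortfall is visible: percentages add to less than 100%, and the number examined can be recovered by summing the frequencies. That works where the categories are exhaustive and exclusive. It does not work for a table of arrhythmia types that has no row for normal, or in which one subject may show several types.

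A reader might also infer several stronger things, which the documents do not support:

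- *Missing subjects are classified as normal.* They fall in no category. For an abnormality rate the arithmetic is the same as counting them free of the finding, but the normal percentage shrinks too.
- *The effect always favours the device.* Favourable echocardiographic categories, such as no or small shunt, are understated by the same factor. Only the abnormal rows look better.
- *The rule contradicts the no-imputation rule.* It fills in no values. It sits badly with an observed-data approach, but it does not breach it.
- *All safety results to year 5 are affected.* Chest X-ray and laboratory tests stop earlier, as shown above.
- *The trial's conclusion is at risk.* Both co-primary endpoints use non-responder imputation, which counts missing subjects against the device in the FAS. High-grade atrioventricular block and residual shunt of 5 mm or more are components of the primary safety endpoint, so through day 360 they are also handled conservatively there.

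**Conclusion.** The concern holds for descriptive by-visit safety tables, as a stated rule that can print misleading percentages. Every category percentage is multiplied by the share of subjects assessed, so abnormality rates can be understated and a decline over visits can be an artefact of missing assessments. The relative understatement equals the missing share: nothing with complete visits, and one fifth at the protocol's 20% ceiling, where 10% becomes 8%, a difference of 2 percentage points.

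This rests on three assumptions: that by-visit categorical tables will be produced, that section 4 will be applied to them literally, and that some assessments will be missing. The 10% rate and the whole-subject example are illustrations. The documents forecast no missing share for individual visits, and 20% is a ceiling for dropout, not an expected value at any visit. Where attrition accumulates, TTE, ECG and vital signs at years 2 to 5 are the results most exposed. The co-primary endpoints and adverse event incidence are unaffected.

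**What to change.** In SAP section 4, keep the analysis-set denominator for the primary endpoints and for adverse event incidence. Add one sentence: for categorical ECG, imaging, laboratory and vital-sign results presented by visit, the denominator is the number of SS subjects with a valid assessment of that item at that visit, and each visit column shows that number and the number missing. This brings categorical tables into line with the count of valid cases already required for continuous variables.

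The cost is one sentence and small changes to table shells. No new data are needed and the success criteria do not change. Some abnormality rates will read slightly less favourably, and favourable categories will rise by the same factor.

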4.1. Analysis data set

Screening refers to subjects who signed the informed consent form and participated in the screening process for this study. Enrollment indicates subjects who met the inclusion/exclusion criteria following assessment.

4.1.1. Full Analysis Set (FAS)

Full analysis set (FAS): According to the basic principles of Intention to Treat (ITT), FAS refers to the set of subjects that comply with the ITT principles. It includes:

- a) Subjects who have been treated with the investigational device, achieved the immediate operation success, and have at least one observation data of primary endpoints after baseline;

- b) Subjects who have received treatment with the investigational device, but have failed in the implantation because of the device itself, regardless of whether there is a study device in the body.

If the implantation is abandoned due to other clinical reasons and there is no investigational device in the body, such subject will not be included in the FAS. The definition of receiving the investigational device treatment is that if any part of the device, including the occluder itself and its delivery device, contact with human body through vascular approach, it can be considered as receiving the device treatment. FAS will be the main data set for baseline data analysis, primary safety, and efficacy evaluation.

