8.9 Subject selection criteria and reasons

- (1) Full analysis set (FAS): According to the basic principles of Intention to Treat (ITT), FAS refers to the set of subjects that comply with the ITT principles. It includes:
- a) Subjects who have been treated with the investigational device, achieved the immediate operation success, and have at least one observation data of primary endpoints after baseline;
 - b) Subjects who have received treatment with the investigational device, but have failed in the implantation because of the device itself, regardless of whether there is test device in the body.

If the implantation is abandoned due to other clinical reasons and there is no investigational device in the body, such subjects will not be included in the FAS. The definition of receiving the investigational device treatment is that if any part of the device, including the occluder itself and its delivery device, contact with human body through vascular approach, it can be considered as receiving the device treatment. FAS will be the main data set for baseline data analysis, primary safety and efficacy evaluation.

- (2) Per protocol set (PPS): refers to subjects who have no serious violation of the study protocol in FAS, have good compliance, have not used drugs or treatments that may affect the efficacy evaluation during the trial, and have no missing data of primary endpoints. Unless otherwise specified, no carrying forward will be performed for the missing data of PPS. Theoretically, PPS should exclude subjects who have not completed all the visit plans due to various reasons, except that whether the subject's ASD has been successfully treated can be judged according to the existing results. PPS will be the secondary data set for efficacy evaluation.
- (3) Safety set (SS): It is used for safety evaluation of the clinical trial, including all subjects who have been treated with the device at least once. SS will be the main data set of safety analysis.
- (4) The efficacy evaluation of the device is mainly based on FAS, and PPS is only used as a reference data set for efficacy evaluation. Safety evaluation is based on SS. According to the above criteria, the subjects will be included in FAS, PPS and SS for interim efficacy evaluation and analysis at 360-day post operation. In the fifth year after operation, the subjects will be also included in FAS, PPS and SS for finally efficacy evaluation

and analysis according to the above criteria.

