4.1.2. Safety Set (SS)

Safety Set will include all subjects who have been treated with the device at least once and have safety evaluation data. SS will be the main data set for other safety analysis excepting the primary safety endpoints.

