4.2. Missing Data and Unreasonable Data

For primary efficacy and safety endpoints, if a subject withdraws from the trial prior to the 360-day follow-up or has missing data for the primary endpoint at the 360-day follow-up, Non-responder Imputation (NRI) will be applied to impute the missing values. For the primary efficacy endpoint of 360-day effective closure rate, if a subject's 360-day follow-up data is missing, that subject will be imputed as “ineffective.” For the primary safety endpoint of common complication

incidence within 360 days post-operation, if a subject's safety follow-up data within 360 days is incomplete due to lost to follow-up or other reasons, that subject will be imputed as having “experienced a common complication.”

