5. ENDPOINTS ANALYSIS

5.1. Primary Endpoints Analysis

For primary efficacy endpoints and safety endpoints, statistical inference will be based on the FAS and PPS. The FAS will serve as the primary dataset for primary endpoint analyses, while the PPS will be the secondary dataset.

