5.1.2. Primary safety endpoints

Primary safety endpoint is defined as the rate of common complications during 360 days post operation. For the primary safety endpoint evaluation, the following hypotheses are tested:

Null hypothesis $H_0: \pi_1 \leq \pi_0$. That is, the Absnow Absorbable Atrial Septal Defect Occluder System fails to meet the design requirement for the 360-day common complications rate.

Alternative hypothesis $H_1: \pi_1 > \pi_0$. That is, the Absnow Absorbable Atrial Septal Defect Occluder System meets the design requirement for the 360-day post-operation common complications rate.

π_1 refers to the expected 360-day post-operation common complications rate, π_0 refers to the Objective Performance Criteria (OPC) value of 360-day post-operation common complications rate.

Statistical inference will be performed using the exact method to estimate the 95% confidence interval (CI) for the common complications rate at 360 days post-operation, as well as the P-value for comparison with the predefined performance goal of 6%. If the upper limit of the two-sided 95% CI for the common complications rate at 360 days is less than 6%, the null hypothesis will be rejected, and it will be concluded that the Absnow Absorbable Atrial Septal Defect Occluder System meets the design requirement for the 360-day post-operation common complications rate. Otherwise, it cannot be concluded that the 360-day common complications rate meets the predefined performance requirement.

If a subject has missing valid data at 360 days, the subject will be imputed as “common complications occurred” using the Non-responder Imputation (NRI) method. For analyses based on the PPS, missing data will not be imputed.

The above two clinical endpoints are designated as primary endpoints for analysis in this study. A conclusion that the Absnow™ Bioresorbable Atrial Septal Defect Occlusion System meets the requirements for clinical application will be made only if both primary endpoints achieve the predefined performance criteria. Therefore, no adjustment to the significance level (α) is required.

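### SAP 4.1.1(a) keeps a post-baseline observation condition that non-responder imputation no longer needs, so a very early loss leaves both co-primary tests instead of counting as a failure (minor)

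*SAP*

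**What the plan says.** SAP 4.1.1(a) defines the first group in the FAS: "Subjects who have been treated with the investigational device, achieved the immediate operation success, and have at least one observation data of primary endpoints after" the pre-implant measurement. Protocol 8.9(1)(a) has the same wording. The two documents differ on missing primary-endpoint data. Protocol 8.7.2 carries the last observation forward (LOCF). SAP 4.2 replaces that with non-responder imputation (NRI), which applies "if a subject withdraws from the trial prior to the 360-day follow-up or has missing data for the primary endpoint at the 360-day follow-up". For closure the missing value becomes a failure. For safety, SAP 5.1.2 says "the subject will be imputed as “common complications occurred” using the Non-responder Imputation (NRI) method".

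On the analysis sets, SAP 5.1 states: "The FAS will serve as the primary dataset for primary endpoint analyses". The Per-Protocol Set is drawn from within the FAS (SAP 4.1.3). The Safety Set does not serve the co-primary safety test: "SS will be the main data set for other safety analysis excepting the primary safety endpoints" (SAP 4.1.2).

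SAP 4 defines baseline as the last valid measurement before the implant. Visit 1 takes place in hospital before discharge and includes echocardiography and a review of common complications (protocol 7.2.4.2). The visit table in protocol 7.2.2 also lists an intraoperative transthoracic echocardiogram. Neither document says what counts as an observation of the primary endpoints.

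**The concern.** Two rules treat nearly the same subject in opposite ways. Imputation can act only on subjects already in the analysis set. A subject lost just after Visit 1 is in the FAS and fails both endpoints. A subject lost after successful release but before any post-baseline assessment is removed before the imputation rule applies, and neither of the other sets brings that subject back into a co-primary test. Death is not one of the seven listed common complications (protocol 7.1.7.1), so an early death without one of them would follow the same path.

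Under LOCF the condition had a purpose, because there must be something to carry forward. Under NRI it has none. Every subject whom it removes from group (a) is one whom SAP 4.2 would score as a failure on both endpoints, so the exclusion can only move both rates towards passing. It also makes membership of a set described as following intention-to-treat depend on data collected after the implant.

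**Working it through.** **Inputs.** Closure: target 99%, performance criterion 94%. Complications: target 1%, criterion 6% (protocol 8.2.1). One-sided alpha 0.025, power 80% (protocol 8.3). Planned N is 146 in the protocol and 142 in SAP 3.1; both are carried through. Decision rule: exact two-sided 95% interval, with lower limit above 94% for closure and upper limit below 6% for complications (SAP 5.1.1, 5.1.2).

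**1. The plan's own figure.** n = [(1.960·√(0.94·0.06) + 0.842·√(0.99·0.01)) / 0.05]² = 120.65, so 121, as stated. 121 × 1.2 = 145.2, rounded up to 146, as stated. The complication test is the mirror image.

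**2. Failures that the exact rule allows.** With x failures in n, the Clopper-Pearson upper limit is the 0.975 quantile of Beta(x+1, n−x). The lower limit for closure is 100% minus that value.
- N=142: 2 failures give 5.00%, pass; 3 give 6.05%, fail.
- N=146: 3 failures give 5.89%, pass; 4 give 6.87%, fail.

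So at most 2 failures are allowed at N=142 and 3 at N=146.

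**3. One early loss with no observation.** All planned subjects are taken as implanted with immediate operation success.

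| N | Other failures | Early loss excluded (FAS rule) | Early loss counted (SAP 4.2 rule) |
|---|---|---|---|
| 142 | 2 | 2/141: 5.03%, pass | 3/142: 6.05%, fail |
| 146 | 3 | 3/145: 5.93%, pass | 4/146: 6.87%, fail |

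Closure mirrors this: lower limits 94.97% against 93.95% at N=142, and 94.07% against 93.13% at N=146.

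**4. When one subject makes no difference.** With one other failure fewer, both versions pass: the less favourable results are 2/142 = 5.00% and 3/146 = 5.89%. With one more, both fail: the more favourable results are 3/141 = 6.09% and 4/145 = 6.91%. One excluded subject therefore matters only when the other failures, including all later losses imputed as failures, total exactly 2 or exactly 3.

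**5. How likely that total is.** Assume 1% true failure and a later loss rate d, so that each remaining subject fails with probability f = 1 − 0.99(1 − d). The values of d are assumed, except for the protocol's 20% maximum dropout (8.4).

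| d | f | P(exactly 2 of 141) | P(exactly 3 of 145) |
|---|---|---|---|
| 0 | 0.0100 | 24.4% | 11.9% |
| 5% | 0.0595 | 0.7% | 1.7% |
| 20% | 0.2080 | effectively 0 | effectively 0 |

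**6. Error rate under assumed early loss.** The documents give no rate e of loss before any observation, so a range is shown. Set the true failure rate, early losses included, at exactly 6%. The number excluded is Binomial(N, e), and the remaining subjects fail with probability (0.06 − e)/(1 − e). The per-endpoint chance of passing is then:

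| e | N=142 | N=146 |
|---|---|---|
| Early losses counted | 0.008 | 0.022 |
| 0.5% excluded | 0.014 | 0.037 |
| 1% excluded | 0.025 | 0.055 |
| 2% excluded | 0.074 | 0.106 |

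**The case against.** The excluded group may be empty. Anything measured after the implant is post-baseline. Group (a) requires immediate operation success, which is itself judged on marker and disc position (protocol 7.1.6.2), and occluder displacement is a component of the safety endpoint. The device procedure in protocol 7.1.4 checks residual shunt by ultrasound, and the visit table lists an intraoperative echocardiogram. If these count, almost nobody is removed. This largely stands, but it is not settled by the text: the visit table first marks common complications at Visit 1, and no definition is given.

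Loss to follow-up before an in-hospital visit is hardly possible, and a death from tamponade, air embolism, cerebral embolism, displacement or high-grade block arguably is an observed event that keeps the subject in. This also stands. It limits the point to an in-hospital death without a listed complication, or a withdrawal, before any assessment. Such a death would still appear in the adverse-event tables (SAP 6.1), though in neither co-primary test.

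The change of verdict sits on an exact count, and steps 4 and 5 confirm it: the later losses that the protocol plans for would normally decide the trial first.

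A reader might go further and infer that only a day-360 result counts as an observation for closure, so that everyone without a day-360 echocardiogram leaves the FAS. The documents do not support this. It would leave NRI in SAP 4.2 and 5.1.1, and LOCF in the protocol, with nothing to act on.

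**Conclusion.** The inconsistency is real on the text, its direction is fixed in favour of the device, and its reach is narrow. It affects few subjects and possibly none. One affected subject changes the verdict only if the other failures total exactly 2 at N=142 or exactly 3 at N=146, which in practice needs nearly complete later follow-up. These counts assume that all planned subjects are implanted with immediate operation success.

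The error rates in step 6 show what the clause would do at assumed early-loss rates of 0.5% to 2%. A reader might take them as evidence that the trial exceeds its 0.025 level, or that early deaths in general escape the analysis. The documents give no early-loss rate and place an in-hospital assessment before discharge, so neither inference holds. Priority is minor.

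**What to change.** In SAP 4.1.1(a), delete the second condition, the one requiring an observation of the primary endpoints after baseline. Every treated subject with immediate operation success is then in the FAS and is imputed under SAP 4.2 when data are missing. The edit does not bring in every subject with a device in the body: one whose implantation failed for a reason other than the device meets neither group (a) nor group (b), and that is a separate matter.

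If protocol 8.9(1)(a) is edited as well, bring protocol 8.7.2 into line with the SAP's NRI at the same time. Otherwise LOCF would apply to subjects with nothing to carry forward.

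Cost: one clause in the SAP, handled under the procedure for SAP changes in protocol 8.8. A matching protocol edit needs ethics committee approval (protocol 12.2). No new data are collected. The reported rates may become slightly less favourable. If no such subject occurs, the results do not change.
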